9.1 Power analysis

Sample size justification. There are no data on liver histological response to curcumin.

The sample size was calculated using A'Hern's single stage phase II methodology⁷⁷ with a significance level of 0.05 (type I error) and power of 0.90 (type II error).

Based on previous trials showing an improvement in surrogate markers of NAFLD with curcumin ranging 20- 50% of patients, depending on different liver disease surrogates, curcumin dose, formulations and treatment duration vs. 15% with lifestyle intervention⁷⁸, the design required 21 evaluable patients in the phytosomal curcumin group; after allowing for a 10% dropout rate, at least 25 subjects per arm were needed to detect a significant difference in the primary outcome. The study A'Hern's design stipulates that at least eight (38%) out of 21 patients in the phytosomal curcumin group have to achieve histological improvement for phytosomal curcumin to be deemed worthy of further investigation with a phase III trial⁸⁴

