5.1 Eligibility criteria

Eligible adult patients (≥ 18 years old) were identified and recruited at the participating trial site centres starting in August 2018 and ending by June 2022, 52 patients will be recruited. Participating trial centres will include the Liver and Metabolic Units at the Humanitas Gradenigo Hospital (Turin) since August 2018), and the Metabolic Unit of Dept of Medical Sciences at the Città della Salute e della Scienza hospital (Turin) since Sept 2018).

All trial participants will give informed written consent at the beginning of the screening visit prior to undergoing any tests and procedures needed to assess eligibility.

Eligibility for the trial will be determined at screening visit 1 by standard blood tests, clinical history (including written-confirmation of drug history where necessary) and physical examination to identify other illnesses or contraindications for participation.

Patients who satisfied the eligibility criteria trial at both sites will be offered to take part in a metabolic mechanistic substudy. The substudy involves a standard Oral Glucose tolerance Test (OGTT) and a standard Oral Fat Tolerance Test (OFTT) on three admissions (at least 24 hours apart from each other) and an indirect calorimetry test at the two participating centres on visits 2 (pretreatment) and 8 (4 weeks

post-treatment). A detailed summary of the metabolic substudy will be published separately. A patient's decision to partake or withdraw from the metabolic substudy will not affect their participation in the main 72-week trial.

A schematic view of trial schedule and design is presented in **Figure 1**.

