9.2 Methods for analysis of primary and secondary outcomes

All evaluable patients will be analysed on an intention-to-treat basis. Evaluable patients are defined as those who have had an end-of-treatment biopsy, irrespective of the amount of treatment they have received.

Patients will be categorised as either achieving the primary histological endpoint (ie, NASH resolution) or not. The proportion of patients with a reported improvement in liver histology will be presented and compared across treatments descriptively with 95% CIs.

The primary analysis will be based on a Cochran–Mantel–Haenszel test based on all randomised patients for the in-trial period with missing data handled as non-responders. The common risk ratio between phytosomal curcumin and placebo was estimated along with exact 95% CI. To test for superiority, the exact two-sided p-value was calculated as the sum of probabilities of outcomes having equal or lower probability than the observed outcome under the null hypothesis.

Adjustments for multiplicity testing in the primary analysis will be performed with the use of the Benjamini-Hochberg procedure; each active-treatment group was compared with the placebo group. Two-sided P values <0.05 were considered statistically significant.

An unpowered, preplanned secondary analysis of categorical outcome measures will be done using the χ^2 test or Fisher exact test, as appropriate, of the difference between the proportions of patients with histological improvement in each treatment group.

A preplanned logistic regression analysis will be undertaken to determine the treatment effect when adjusted for the stratification variables (diabetes status, obesity status, fibrosis stage, CKD status) and trial site. We will calculate adjusted relative risks using the Mantel-Haenszel test. Two-sided P values <0.05 will be considered statistically significant in all analyses.

Continuous secondary outcome measures will be compared between treatment groups using linear

regression, adjusting for parameter baseline values and allocated treatment (as model covariates, equivalent to ANCOVA), with multilevel modelling for key continuous outcome measures to account for repeated measures within each patient.

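### The 0.90 power in Section 9.1 belongs to a one-arm A'Hern screen; the two-arm exact test that is primary in Section 9.2 does not have it

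*Protocol*

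**What the plan says.** Section 9.1 names its method: "The sample size was calculated using A'Hern's single stage phase II methodology", "with a significance level of 0.05 (type I error) and power of 0.90 (type II error"). Its planning rates are "improvement in surrogate markers of NAFLD with curcumin ranging 20- 50% of patients" "vs. 15% with lifestyle intervention". From these it concludes that "the design required 21 evaluable patients in the phytosomal curcumin group", with at least 8 of the 21 needing to respond for curcumin to merit a phase III trial. Placebo plays no part in that rule. After a 10% dropout allowance, the section says that "at least 25 subjects per arm were needed to detect a significant difference in the primary outcome".

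Section 5.1 sets the total: "52 patients will be recruited". At the 1:1 allocation of Section 5.5 this is 26 per arm.

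Section 9.2 makes a CMH test primary, "based on all randomised patients for the in-trial period with missing data handled as non-responders". It tests superiority over placebo with an exact two-sided p-value at the 0.05 level. The same section calls the secondary chi-square or Fisher comparison of proportions unpowered, but does not say this of the primary test.

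**The concern.** A'Hern's design compares one arm with a fixed rate by a one-sided exact binomial test. Its power says nothing about a comparison with a concurrent placebo arm. That comparison also carries the sampling error of the control arm, a two-sided level, and the shrinkage of both rates when missing biopsies count as failures. None of these enters the calculation in Section 9.1, yet the closing clause presents 25 per arm as the number needed for a significant difference.

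The stake is how the primary result will be read. A reader who carries the 0.90 over to the CMH test would give a non-significant result more weight as evidence against curcumin than the design can support. The two criteria can also disagree. If 8 of 21 curcumin patients and 3 of 21 placebo patients (14%) responded, the screening rule would be met, while the exact two-sided p-value would be about 0.16.

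**Working it through.** **Inputs.** Section 9.1: alpha 0.05, power 0.90, 21 evaluable, at least 8 responders, curcumin 20-50%, comparator 15%, dropout 10%. Sections 5.1 and 5.5: 52 patients at 1:1, so 26 per arm. Section 9.2: exact two-sided test at 0.05, missing counted as non-response.

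**Step 1: reproduce the plan's own figure.** Search for the smallest n, with cut-off r, such that P(X ≥ r | n, p0) ≤ 0.05 and P(X ≥ r | n, p1) ≥ 0.90, where X is binomial.

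| p0 | p1 | n | r |
|---|---|---|---|
| 0.20 | 0.50 | 21 | 8 |
| 0.15 | 0.50 | 14 | 5 |
| 0.15 | 0.45 | 21 | 7 |

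The pair 0.20 and 0.50 returns the stated rule: P(X ≥ 8 | 21, 0.20) = 0.043 and P(X ≥ 8 | 21, 0.50) = 0.905. The printed 15% does not return it. So the 0.90 is the one-arm power, and the null that fits is 20%. That null is inferred, because the protocol prints 20% only as the lower end of the curcumin range. The dropout step is acceptable: 21/0.9 = 23.3, rounded up to 24, against a stated minimum of 25.

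**Step 2: power of the two-arm test.** For every pair (x, y) of responder counts at 26 per arm, compute the conditional exact two-sided p-value as the sum of probabilities of outcomes no more likely than the one observed. Then sum Bin(x; 26, p1) × Bin(y; 26, p0) over tables with p < 0.05 in favour of curcumin. No stratification is modelled. For 10% missing counted as non-response, multiply both rates by 0.9: 0.50 becomes 0.45, 0.15 becomes 0.135 and 0.20 becomes 0.18. The uncorrected, unstratified CMH test is enumerated in the same way.

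| True rates | Missing | Exact two-sided | Uncorrected CMH |
|---|---|---|---|
| 50% vs 15% | none | 0.71 | 0.79 |
| 50% vs 15% | 10% | 0.62 | 0.72 |
| 50% vs 20% | none | 0.54 | 0.63 |
| 50% vs 20% | 10% | 0.45 | 0.56 |

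These rows use the top of the quoted curcumin range. At 35% vs 15% with nothing missing, the exact test has power 0.27.

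**Step 3: what 26 per arm can detect with the exact test at 80% power.** The rates are true rates before imputation.

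| Comparator | No missing | 10% counted as non-response |
|---|---|---|
| 15% | about 54% | about 58% |
| 20% | about 60-61% | about 64% |

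**Step 4: size for 90% power, exact test, curcumin at 50%.** Against 15%: 41 per arm with nothing missing, 47 with 10% counted as non-response. Against 20%: 58 and 67. These show the scale of the gap and are not a request for more patients.

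**The case against.** The strongest reply is that this is a phase II screen and the protocol partly says so. Section 9.1 attaches alpha and power to A'Hern's method, sizes the curcumin group alone, and gives a within-arm rule for moving to phase III. Section 9.2 speaks of comparing proportions descriptively with confidence intervals and labels the chi-square or Fisher analysis unpowered. No sentence assigns 0.90 to the CMH test by name. All of this is correct, and it limits the misstatement to the closing clause about 25 per arm. It does not remove it: the CMH superiority test is still primary, the label of unpowered is kept for a secondary analysis, and the clause speaks of a significant difference with both arms counted.

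Three stronger readings are tempting and go too far.

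- A reader might infer that the trial would miss a true effect about half the time. That follows only for 50% vs 20%, and the 20% is back-solved. At the printed 15% the miss rate is 29% with no missing data and 38% with 10% counted as non-response.
- A reader might take 45-71% as the power of the planned test. It is conditional on curcumin at 50%, 26 per arm and an unstratified exact test. Section 9.2 does not name the CMH strata. Randomisation uses four binary factors, so up to 16 cells for 52 patients, and a rise to 0.90 from stratifying is implausible.
- A reader might conclude that the 8/21 rule is wrong. As a one-arm screen of 20% against 50% it is valid.

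**Conclusion.** The point holds in this form. The 0.90 in Section 9.1 is the power of a one-arm rule, and the statement that 25 per arm suffices to detect a significant difference is unsupported for the primary test in Section 9.2. At 26 per arm, with curcumin at 50% and an unstratified exact test, power is about 0.62-0.71 against the printed 15% and about 0.45-0.54 against the inferred 20%. The lower figure in each pair counts 10% as non-responders, equally in both arms. A less conservative uncorrected CMH test stays at or below about 0.79. Lower curcumin rates within the quoted range give less power. The direction does not depend on which comparator rate is chosen. The size does, which is why the disagreement between 15% and the implied 20% has to be settled in the text.

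**What to change.** Keep 52 patients, the endpoint and the test, and restate Section 9.1:

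- Confine alpha 0.05 and power 0.90 to the within-arm 8/21 rule, and print its null and target rates. The rule fits 20% vs 50% (exact alpha 0.043, power 0.905). Reconcile this with the printed 15%, which would give 5/14 against 50% or 7/21 against 45%.
- Delete the clause that ties 25 per arm to detecting a significant difference.
- State the power of the two-arm primary test with its assumptions: about 45-62% with curcumin at 50%, a comparator of 20% or 15%, 26 per arm, an unstratified exact test and 10% counted as non-response.
- On the same basis, give the difference detectable at 80% power: about 58% vs 15% or 64% vs 20%, as true rates before imputation. The smaller differences (54% vs 15%, 60-61% vs 20%) apply only if no biopsies are missing and should be labelled so.

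The cost is one reworded paragraph and a less favourable stated power. No patients are added.

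### The phase III go rule (8 of 21 on curcumin) states no null or target rate, gives no cutoff for other evaluable numbers, and is not tied to the placebo comparison

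*Protocol*

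**What the plan says.** Section 9.1 (Power analysis) of the protocol gives the method: "The sample size was calculated using A'Hern's single stage phase II methodology", with type I error 0.05 and power 0.90. For rates, it cites earlier trials "showing an improvement in surrogate markers of NAFLD with curcumin ranging 20- 50% of patients", set against a comparator: "vs. 15% with lifestyle intervention". It labels none of these as the null or the target rate, and it says that no histological response data exist for curcumin. It concludes that "the design required 21 evaluable patients in the phytosomal curcumin group", and raises this to at least 25 per arm for 10% dropout. The go condition follows: "at least eight (38%) out of 21 patients in the phytosomal curcumin group have to achieve histological improvement" before curcumin is taken to phase III.

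Section 5.1 gives the total: "52 patients will be recruited". Section 5.5 allocates 1:1. Section 9.2 counts as evaluable anyone with an end-of-treatment biopsy. It makes the primary analysis a Cochran–Mantel–Haenszel (CMH) comparison with placebo in all randomised patients, with missing outcomes counted as non-response: "To test for superiority, the exact two-sided p-value was calculated". Section 9.2 does not mention the go rule, and the go rule in 9.1 does not mention placebo.

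**The concern.** Three things are left open in a rule that decides whether a phase III trial is recommended.

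- **The inputs.** A reader who takes the printed 15% as the null cannot recover 21 and 8. The 20% that does reproduce them appears only as the low end of the response range on curcumin.
- **The denominator.** The trial recruits more than 21 per arm, and the evaluable number depends on how many patients have the second biopsy. The protocol does not say what applies when it is not 21.
- **The control arm.** A single-arm threshold compares curcumin with an assumed historical rate although randomised placebo patients are available. If lifestyle advice or regression to the mean raises response in both arms, the count can be reached with no treatment effect.

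At stake is a phase III recommendation whose error rate is unknown and which could rest on a response that placebo patients share.

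**Working it through.** **Inputs.** From section 9.1: alpha 0.05 (taken as one-sided, as is usual for A'Hern), power 0.90, rates of 15%, 20% and 50%, cutoff 8 of 21, dropout 10%. From sections 5.1 and 5.5: 52 patients at 1:1, so 26 per arm. No placebo histology rate is given, so a range of 15% to 30% is assumed below.

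**Formula.** A'Hern's design takes the smallest n, with cutoff r, such that P(X ≥ r | n, p0) ≤ 0.05 and P(X ≥ r | n, p1) ≥ 0.90, where X is binomial.

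**Step 1: reproduce the plan's figure.**

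| p0 | p1 | n | r | alpha | power |
|---|---|---|---|---|---|
| 20% | 50% | 21 | 8 | 0.0431 | 0.9054 |
| 15% | 50% | 14 | 5 | 0.0467 | 0.9102 |
| 15% | 45% | 21 | 7 | 0.0287 | 0.9036 |

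On a grid of 5-point steps, only 20% versus 50% gives 21 with 8. Off the grid, 19% versus 50% and 20% versus 51% also do, so the inputs are about 20% and 50%.

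**Step 2: expected denominator.** 25 × 0.9 = 22.5 and 26 × 0.9 = 23.4, so about 23 rather than 21.

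**Step 3: 8 read as a fixed count.** P(X ≥ 8):

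| Evaluable n | 15% null | 20% null | power at 50% |
|---|---|---|---|
| 19 | 0.004 | 0.023 | 0.820 |
| 20 | 0.006 | 0.032 | 0.868 |
| 21 | 0.008 | 0.043 | 0.905 |
| 22 | 0.011 | 0.056 | 0.933 |
| 23 | 0.015 | 0.072 | 0.953 |
| 24 | 0.020 | 0.089 | 0.968 |
| 25 | 0.026 | 0.109 | 0.978 |
| 26 | 0.032 | 0.131 | 0.986 |

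**Step 4: rule read as 38%.** The cutoff becomes 9 at n = 22 and 23, and 10 at n = 24 to 26. Alpha at 20% is then 0.020, 0.027, 0.013, 0.017 and 0.023. Power at 50% is 0.857, 0.895, 0.846, 0.885 and 0.916, so it is below 0.90 from n = 22 to 25.

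**Step 5: no difference between arms.** With the same true rate in both arms and a fixed count of 8, the probability of a go is:

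| Common rate (assumed) | n = 21 | n = 23 |
|---|---|---|
| 15% | 0.01 | 0.02 |
| 20% | 0.04 | 0.07 |
| 25% | 0.13 | 0.20 |
| 30% | 0.28 | 0.38 |

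Single outcomes show the same. A result of 8/21 versus 8/21 meets the rule with no difference at all, and 8/21 versus 4/21 meets it with a two-sided Fisher p of 0.31.

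**Step 6: cutoffs that hold alpha at 20% to at most 0.05.**

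| Evaluable n | cutoff | alpha at 20% | power at 50% |
|---|---|---|---|
| 19 | 8 | 0.023 | 0.820 |
| 20 | 8 | 0.032 | 0.868 |
| 21 | 8 | 0.043 | 0.905 |
| 22 | 9 | 0.020 | 0.857 |
| 23 | 9 | 0.027 | 0.895 |
| 24 | 9 | 0.036 | 0.924 |
| 25 | 9 | 0.047 | 0.946 |
| 26 | 10 | 0.023 | 0.916 |
| 27 | 10 | 0.030 | 0.939 |

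**The case against.** There are five fair points in favour of the plan.

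- **At the printed comparator the rule is safe.** With a 15% null, a count of 8 has type I error of at most 0.032 up to n = 26. A reader might infer that the rule is valid only at exactly 21 patients and a 20% null. That goes too far: at 15% it is conservative.
- **The rule also prints a percentage.** Scaled at 38%, it keeps alpha at 20% below 0.05, at some cost in power. The inflation in step 3 therefore depends on reading 8 as a fixed count, and the text does not settle which reading applies.
- **A 30% placebo response is an assumption.** Nothing in the protocol supports it, so the 0.28 and 0.38 are the upper end of an assumed range. On the 38% reading, the figure at 30% and n = 23 is 0.23.
- **The trial does not ignore placebo.** Section 9.2 labels the CMH comparison as the primary analysis. A reader might infer that efficacy itself will be judged on the curcumin arm alone. The protocol does not say that. The count governs only the step to phase III, and its wording can be read as a necessary condition.
- **Frequent disagreement with the superiority test is weak evidence against the rule.** At 50% versus 20% with 23 per arm, the count is met with a non-significant Fisher test in 49% of trials. But Fisher is non-significant in 54% of such trials anyway (power 0.462). This mostly reflects low two-arm power in trials where curcumin works, so it does not show false go decisions.

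All five stand as limits on size. None of them supplies the missing design rates, the cutoff for other denominators, or a link from the go decision to placebo.

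**Conclusion.** The point holds in a limited form. The go rule is under-specified and, as written, can be met with no difference from placebo. Its figures match about 20% versus 50%, not the 15% printed as comparator. At the expected 23 evaluable patients, a fixed count of 8 has type I error 0.072 at a 20% null and 0.015 at 15%. Read as 38%, alpha at 20% holds, but power at 50% is 0.895.

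The chance of a go without any treatment effect is material only if the common response rate is about 20% or more. It runs from 0.02 at 15% to 0.38 at 30% with 23 evaluable patients. These figures assume binomial responses, a fixed count, 10% dropout and the stated range of common rates. The primary efficacy analysis against placebo is not affected.

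**What to change.** In section 9.1:

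1. State p0 = 0.20 and p1 = 0.50 as the design inputs, with their basis, and explain how they relate to the 15% comparator.
2. Replace the single count by the cutoff for the number evaluable: 8 for 19 to 21, 9 for 22 to 25, 10 for 26 to 27. Alpha at 20% is then at most 0.05. Note that power at 50% is below 0.90 at n = 19, 20, 22 and 23.
3. State that reaching the count is necessary but not sufficient, and that a phase III recommendation also rests on the observed difference from placebo and its 95% CI.

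The cost is protocol wording and a slightly stricter go threshold. No patients or procedures are added.

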9.2 Methods for analysis of primary and secondary outcomes

All evaluable patients will be analysed on an intention-to-treat basis. Evaluable patients are defined as those who have had an end-of-treatment biopsy, irrespective of the amount of treatment they have received.

Patients will be categorised as either achieving the primary histological endpoint (ie, NASH resolution) or not. The proportion of patients with a reported improvement in liver histology will be presented and compared across treatments descriptively with 95% CIs.

The primary analysis will be based on a Cochran–Mantel–Haenszel test based on all randomised patients for the in-trial period with missing data handled as non-responders. The common risk ratio between phytosomal curcumin and placebo was estimated along with exact 95% CI. To test for superiority, the exact two-sided p-value was calculated as the sum of probabilities of outcomes having equal or lower probability than the observed outcome under the null hypothesis.

Adjustments for multiplicity testing in the primary analysis will be performed with the use of the Benjamini-Hochberg procedure; each active-treatment group was compared with the placebo group. Two-sided P values <0.05 were considered statistically significant.

An unpowered, preplanned secondary analysis of categorical outcome measures will be done using the χ^2 test or Fisher exact test, as appropriate, of the difference between the proportions of patients with histological improvement in each treatment group.

A preplanned logistic regression analysis will be undertaken to determine the treatment effect when adjusted for the stratification variables (diabetes status, obesity status, fibrosis stage, CKD status) and trial site. We will calculate adjusted relative risks using the Mantel-Haenszel test. Two-sided P values <0.05 will be considered statistically significant in all analyses.

Continuous secondary outcome measures will be compared between treatment groups using linear

regression, adjusting for parameter baseline values and allocated treatment (as model covariates, equivalent to ANCOVA), with multilevel modelling for key continuous outcome measures to account for repeated measures within each patient.

We estimated mean annual rates of change in eGFR from baseline to the final follow-up visit (total slopes), by treatment allocation using linear mixed model repeated measures (MMRM); adjustments were made for age, sex, first baseline CKD stage, baseline eGFR; baseline urinary ACR, diabetes, history of cardiovascular disease, systolic blood pressure, angiotensin-converting enzyme/angiotensin receptor blocker use⁷⁹

Proteinuria will be estimated using measurements of urinary protein and creatinine at baseline and at baseline and at each visit thereafter.

Albuminuria and eGFR stage will be categorized according to the KDIGO classification system⁸⁰

The end-stage renal disease was defined as kidney transplantation or the receipt of dialysis for at least 30 days unless death occurred.

For exploratory outcomes, we will explore the existence of a threshold in hepatic NF-kB activation change predicting histological response (NASH resolution, fibrosis improvement) using the area under receiver operating characteristic curve (AUROC) analysis and Youden index.

A sensitivity analysis will be performed in which missing data were handled by reference-based multiple imputation informed by data from placebo recipients (see **Preplanned subgroup and sensitivity analyses suhealing**).

Safety will be analysed descriptively

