Preliminary human data indicate curcumin supplementation improves surrogate markers of liver disease and of metabolic risk in NAFLD patients^{20, 21}. The combination of curcumin with phospholipids greatly improves oral bioavailability of curcumin, allowing greater systemic concentrations and delivery to target organs^{22, 23}, and curcumin-phosphatidylcholine phytosome complex administration for up to 18 months was well-tolerated, safe²⁴ and improved clinical end-points and inflammatory parameters in patients with osteoarthritis, uveitis and chronic kidney disease (CKD)^{25, 26, 27}.

2. Research Hypothesis and Aims

On the basis of above-mentioned data, we hypothesized that treatment with phytosomal curcumin would result in significant improvement in liver histology in patients with NASH.

Key secondary hypotheses include tolerability and safety of phytosomal curcumin and the potential to improve NASH-related CKD, systemic inflammation, glucose and lipid metabolism.

To test this hypothesis, we designed a phase II, multicentre, double-blinded, placebo-controlled randomized controlled trial (RCT).

3. Study Design setting and timeline

This is a 72-week, investigator-initiated, multicentre, randomized, double-blinded, placebo-controlled trial of treatment with phytosomal curcumin 1 g daily for adults with biopsy-proven NASH. Screening was undertaken within 14 days of randomisation to assess eligibility and collect baseline data. Patients who satisfied the eligibility criteria were randomly assigned (1:1) to receive oral phytosomal curcumin 1 g daily (experimental) or placebo (control). After which, a 12-week washout period is scheduled.

The trial will be conducted at two University hospitals (HUMANITAS Gradenigo, Turin, Italy, and Città della Salute e della Scienza, Turin, Italy) between May 25th, 2018 and Dec 30th, 2022.

The primary outcome measure will be assessed using an intention-to-treat analysis of the proportion of evaluable patients achieving an improvement in liver histology between liver biopsies at baseline (within 6 months of screening) and after 72 weeks of treatment. Histological improvement will be defined as a

combination of resolution of active steatohepatitis and no worsening in fibrosis (assessed by Kleiner Fibrosis score²⁸; detailed in outcome section).

4. Ethics and regulatory approval

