9.3 Methods in analysis to handle missing data

The primary imputation method for missing data will be the non-responder imputation for primary and secondary dichotomous outcomes. This approach does not rely on an assumption of missing at random and is considered conservative for estimating the treatment effect.

To investigate the sensitivity of the histological results with regard to the handling of missing

data, post-hoc sensitivity analyses using multiple imputation will be conducted. These analyses are based on the same CMH method as for the main analyses but using a multiple imputation at random method for missing data(see following Subheading)

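### The primary outcome is tied to biopsied patients in one place and to all randomised patients in another, and the biopsied set is wrongly called intention-to-treat

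*Protocol*

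**What the plan says.** **Biopsied patients.** Protocol Section 3 says the primary outcome will be "assessed using an intention-to-treat analysis of the proportion of evaluable patients achieving an improvement in liver histology between liver biopsies" at baseline and after treatment. The first paragraph of Section 9.2 repeats the label: "All evaluable patients will be analysed on an intention-to-treat basis". It then defines the set: "Evaluable patients are defined as those who have had an end-of-treatment biopsy, irrespective of the amount of treatment they have received". Section 9.1 states the sample size as 21 evaluable patients in the curcumin arm and sets the go rule at 8 or more responders among those 21.

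**All randomised patients.** Later in Section 9.2 the primary analysis is a CMH test "based on all randomised patients for the in-trial period with missing data handled as non-responders". Section 9.3 agrees: "The primary imputation method for missing data will be the non-responder imputation for primary and secondary dichotomous outcomes". Section 9.5 repeats this and contrasts its reference-based imputation with the primary analysis.

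**Multiplicity.** Section 9.2 also says: "Adjustments for multiplicity testing in the primary analysis will be performed with the use of the Benjamini-Hochberg procedure", comparing each active group with placebo. Section 5.5 has one active group and Section 7 has one primary outcome.

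**The concern.** The two descriptions cannot both define the primary analysis. Everyone in the biopsied set has had the biopsy that supplies the outcome, so imputing non-response for an absent biopsy has nothing to act on there. Non-responder imputation only has meaning if patients without a second biopsy are kept in.

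The label is also wrong on any reading. Whether a patient has a second biopsy at week 72 is decided after randomisation and may depend on tolerability, response or withdrawal. Conditioning on it gives a complete-case set, and ignoring how much treatment was taken does not turn that set into intention-to-treat.

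At stake are the denominator of the headline response rates, the risk ratio when the arms lose different numbers of biopsies, and, in a trial of 52 patients, the side of 0.05 on which the p-value falls.

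**Working it through.** **Inputs from the protocol.** 52 patients (5.1), randomised 1:1 (5.5), so 26 per arm. Planned dropout 10%; 21 evaluable in the active arm; go if at least 8 respond; curcumin surrogate response 20–50%, lifestyle 15% (all 9.1). Two-sided 0.05 (9.2).

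**Assumptions.** Responder counts and the split of missing biopsies are mine. Fisher's exact test without strata stands in for the exact stratified CMH test. 10% of 52 is 5.2, so I take 5 missing biopsies.

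**The plan's own figure.** The single-stage design does not name its null and target rates. Taking the ends of the quoted range, p0 = 0.20 and p1 = 0.50:

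- P(X ≥ 8 | n = 21, p = 0.20) = 0.043, within 0.05.
- P(X ≥ 8 | n = 21, p = 0.50) = 0.905, above 0.90.
- No smaller n meets both limits, so 21 and 8 reproduce exactly.
- 21 / 0.90 = 23.3, hence 24, against the stated minimum of 25 per arm.

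The rule is thus calibrated to 21 patients with a biopsy. Eight responders are 8/21 = 38.1% of that set but 8/26 = 30.8% of the randomised arm. If all 26 had a biopsy and the threshold stayed at 8, the false-go probability at p = 0.20 would be P(X ≥ 8 | n = 26) = 0.131.

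**Effect of the population on the comparison.** Evaluable rate = responders / biopsied; all-randomised rate = responders / 26.

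| Missing (active, placebo) | Evaluable | p | All randomised | p |
|---|---|---|---|---|
| 3, 2 | 11/23 v 4/24 (RR 2.87) | 0.031 | 11/26 v 4/26 (RR 2.75) | 0.064 |
| 0, 5 | 9/26 v 2/21 (RR 3.63) | 0.081 | 9/26 v 2/26 (RR 4.50) | 0.038 |
| 3, 3 | 10/23 v 3/23 (RR 3.33) | 0.047 | 10/26 v 3/26 (RR 3.33) | 0.052 |

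The first row loses significance on moving to all randomised patients, and the second gains it. In the third, with equal losses, the risk ratio does not change; the rates and the p-value do.

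**How often it matters.** I fixed 3 active and 2 placebo biopsies missing, drew responders among the biopsied as binomial with 40%, 45% or 50% (active) and 15% (placebo), and summed the exact probability that the two sets disagree at 0.05. The results are 14.9%, 15.3% and 13.8%. The two sets agree in about 85% of such trials.

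**Multiplicity sentence.** With m = 1 test, Benjamini-Hochberg compares the smallest p-value with (1/1) × 0.05 = 0.05. Nothing changes.

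**The case against.** The strongest reply is that the protocol largely answers the question itself. Only one analysis carries the name primary, the CMH test on all randomised patients. Section 9.3 backs it, and the contrast drawn in 9.5 makes sense only if patients without week-72 histology are in the primary analysis. In 9.2 the evaluable definition leads into proportions presented descriptively with confidence intervals, with no test attached.

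Much of this stands. A reader might infer that there are two primary results of equal standing, either of which could be reported as prespecified. The text does not go that far. But the reply does not clear the conflict: Section 3 attaches the primary outcome itself to evaluable patients, no sentence calls the evaluable analysis supportive, and the go rule uses that set.

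A reader might also infer that using all randomised patients must make the result less favourable. It need not: the direction depends on which arm loses biopsies, as the second row of the table shows, and equal losses leave the risk ratio alone.

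Finally, a misplaced Benjamini-Hochberg sentence might suggest that the secondary histological outcomes need a formal multiplicity procedure. The documents do not support that as an error. This is a 52-patient phase II trial, 9.2 describes its secondary categorical analysis as unpowered, and such control is often left to the SAP, which is not shown. Family-wise error figures that assume independence would also overstate the problem, because several of the fibrosis outcomes overlap.

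**Conclusion.** The point holds as a conflict in the current text about the population for the primary outcome, together with a wrong intention-to-treat label. The all-randomised analysis is the better-supported reading but is not stated as the only one, and the 8-of-21 rule sits on the other denominator.

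The conflict has consequences only if biopsies are missing, which the planned 10% dropout anticipates. At about that level it can reverse the significance call in either direction; under one assumed pattern (3 active and 2 placebo missing, response 40–50% against 15%) it does so in about 14–15% of trials. These sizes rest on assumed counts and an unstratified test, so they show what is possible and do not predict the result. The contradiction itself needs no assumption. The Benjamini-Hochberg sentence is leftover text with no effect on the primary test.

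**What to change.** 1. In Section 3 and Section 9.2, name all randomised patients, with missing histology counted as non-response, as the sole primary population.
2. Call the biopsied set a supportive complete-case analysis and remove the intention-to-treat label from it in both places.
3. In Section 9.1, state which denominator the 8-of-21 rule uses and how it is applied if the number of biopsied patients in the active arm is not 21.
4. Delete the Benjamini-Hochberg sentence for the primary test.

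The cost is protocol wording only, with no new patients, visits or data. The analysis already named primary does not change. Item 3 needs a short decision by the statistician, because the threshold was calibrated to 21 evaluable patients.
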